1. INTRODUCTION

Severe Acute Respiratory Syndrome Coronavirus 2 (SARS-CoV-2) has been identified as the cause of the pandemic outbreak of the coronavirus disease 2019 (COVID-19). Boehringer Ingelheim (BI) has launched a large-scale RT-PCR confirmation programme called COVID-19 Tests to counter the pandemic and safeguard public health. This dedicated health care measure was developed to complement the actions implemented by public health care to relieve the efforts of the health authorities.

The global pandemic COVID-19 is a reportable disease in most countries and local health authorities are monitoring the contacts of infected individuals to detect potential additional infections in order to prevent the spread. Contact tests generally depend on the presence of certain respiratory symptoms which coincide with the established risk criteria for increasing the probability of a positive nucleosides (RNA) result for SARS in swabs or sputum samples **[RKI 2020]**. It is therefore assumed that tests must be performed on as many individuals as possible in order to contain the pandemic situation. As such, the sampling method has become a critical factor, as it is more difficult to take swab samples than to collect saliva, and sampling must be optimised to allow more flexibility in obtaining samples for virus RNA identification, regardless of the availability of medical staff and testing centres. Furthermore, a method that could be performed at home and during quarantine will prevent the spread and reduce the biosafety risk in general.

1.1 MEDICAL BACKGROUND

SARS-CoV-2 belongs to the *Coronaviridae* family, which also includes members that cause the common cold, Severe Acute Respiratory Syndrome (SARS) and Middle East Respiratory Syndrome (MERS) **[Liu et al. 2020]**.

It has been confirmed that the novel coronavirus is transmitted from person to person. Close contact between individuals (< 1.5 m) promotes the spread of the virus and, as a result, the disease. It is spread predominantly through droplets expelled when coughing or sneezing, but also through atomised particles when speaking. It must be assumed that transmission takes place when kissing, shaking hands or touching contaminated surfaces in public spaces (public transport, door handles, buttons, etc.), particularly when touching the mouth, nose or eyes afterwards. Given the many uncertainties regarding SARS-CoV-2 infection to date, including the dispersion factor (K), it is important to closely monitor the social setting and conduct extensive tests to control the pandemic situation.

COVID-19 symptoms can vary from very mild to severe and may include fever, cough, breathing difficulty and fatigue, which commonly occur after an incubation period of 2 to 14 days **[Huang et al. 2020]**. These symptoms can become serious and include fatal outcomes. It is thought that approximately 20% of infected patients show non-specific symptoms or no symptoms at all, but can still spread the virus **[He et al. 2020]**. Unless they are quickly identified by means of sufficient, potentially regular off-site detection activities, these individuals have a high risk of unwittingly transmitting SARS-CoV-2, which is a significant threat to public health against a backdrop of acute infection driven by an on-demand test scheme. It is understood that the burden of regular tests cannot be applied to all, but rather to selected groups.

There is not yet a vaccine available for SARS-CoV-2, nor are there any specific antiviral drugs for COVID-19. The standard treatment is targeted primarily at relieving the symptoms, while compassionate use of medications is limited mainly to clinical studies, as well as invasive measures to save lives in severe cases, which often require long-term intensive care. The long-term impact of

COVID-19 on health cannot be evaluated at this early stage of the disease, but emerging evidence suggests that the infections can cause serious harm and potentially cause sequelae with a negative impact on overall health [RKI 2020]. As such, a test strategy with the diagnostic tools available for prevention or early diagnosis of COVID-19 is essential as an additional measure to the rules in place, such as social distancing and hygiene to prevent uncontrolled spread, to prevent the health services from collapsing and to reduce the long-term impact on public health.

1.2 DIAGNOSTIC PROFILE

The standard laboratory test for diagnosing SARS-CoV-2 is an RT-qPCR certified protocol to identify the RNA of the virus in swab samples (nasopharyngeal/oropharyngeal) or sputum samples [Udugama et al. 2020].

1.2.1 Quantitative reverse transcription polymerase chain reaction (RT-qPCR)

RT-qPCR is a bioanalytical method for detecting nucleosides (DNA or RNA) in a wide range of test samples (e.g. blood, saliva and swabs). The technique is based on the *in vitro* amplification of genetic material using complementary nucleoside fragments (primers) and specific enzymes (polymerases). While the original material is undetectable due to its low concentration, the amplification can easily be detected, e.g. by means of gel electrophoresis or, in the case of RT-qPCR, automatically by digitally measuring a fluorescent signal in the device. There is currently a wide range of modified RT-qPCR techniques available for various situations. For RNA detection (SARS-CoV-2 genome), another specific enzyme is required: reverse transcriptase (RT). There is a RT-PCR protocol available from Charité Virology for diagnosing COVID-19 [Corman et al. 2020]. The **Kylt® for detection/confirmation of SARS-CoV-2** (PCR) kit is based on the PCR method published by Corman et al., which detects specific E gene sequences, and specific sequences in the second PCR of the RdRP gene and the S gene of SARS-CoV2.

A second test kit with RT-PCR is the **TaqPath™ COVID-19 CE-IVD RT-PCR kit**, provided by [REDACTED], which uses three different specific sequences of SARS-CoV-2 in the ORF1ab, N and S genes of the virus, for a multiplex detection focus.

The **cobas® SARS-CoV-2 (PCR) test**, by [REDACTED] is a PCR detection system which is fully automated for the **cobas® 6800/8800** laboratory systems. This PCR detects in parallel a fragment of the E gene of the pan-Sarbecovirus and a specific ORF1 sequence of SARS-CoV-2, and is validated for nasopharyngeal and oropharyngeal samples taken with swabs and collected in UTM.

The three PCR kits include an internal positive control (IPC) which targets the RNA of human β -actin as an endogenous or externally added control, or externally added control targets in each reaction to validate the polymerase reaction.

1.3 JUSTIFICATION

In order to effectively test and monitor, reliable diagnostic tools must be selected, implemented and regularly performed. The results must be evaluated in relation to the medical history and clinical evidence. RT-qPCR is the standard for identifying SARS-CoV-2 infection and for detecting viral RNA, generally when the medical staff take nasopharyngeal swab samples. This is considered to be an established procedure and is expected to provide reliable results; however, it has been found that the procedure depends on participant cooperation and staff experience. Furthermore, self-sampling is not considered optimal and may produce false-negative results due to the difficulty of the technique

and the high level of variability due to human factors. In some cases it is difficult or impossible to obtain suitable samples. Furthermore, as there is no need to go to special centres, there is a lower risk of spreading the virus. It also significantly reduces biosafety and risk of infections for medical staff when taking swab samples.

The Salivette® Cortisol device will be used to collect saliva from the patient due to its high capacity to stimulate salivation and absorb saliva. In this saliva sample, it is expected to find SARS-CoV-2 viral RNA which will be identified through processing with the RT-qPCR technique, as described for the nasopharyngeal mucosa swab samples. No cortisol measurements will be performed in the collected sample.

1.4 RISK-BENEFIT ASSESSMENT

The Salivette® Cortisol device, which is placed in the mouth and gently chewed for approximately 60 seconds, is considered to be very low risk. Its taste may be considered unpleasant. It is handled by the participant and, as such, there is no additional risk expected for the medical staff. During the tests, everyone wears masks in the rooms while the swab samples are taken, and the medical staff are protected with FFP2 masks, protective clothing and double gloves. Sampling with Salivette® Cortisol can be performed on-site. The layout of the room will follow the general distancing and hygiene measures in place, and surfaces will be cleaned and disinfected in line with procedure after each participant leaves. The risk of harm, such as sequelae due to the medical procedure, and the risk of infection of all participants, including the occupational health care team, was assessed before the tests and was considered highly unlikely.

There is recent evidence (Wyllie, AL et al. 2020. <https://doi.org/10.1101/2020.04.16.20067835doi>) that saliva sampling potentially produces more reliable results when compared to swab sampling.

Conclusions: It is considered necessary to establish sampling methods other than swab samples in order to reduce the biosafety risk and increase the flexibility of tests and their acceptance among potentially infected individuals, as taking swab samples is more invasive than collecting samples with Salivette® Cortisol. The sampling method established should allow for regular tests and be easy and well accepted by patients, while providing comparable results.

Risks and methods related to the medical procedure

There are some risks involved in the nasopharyngeal mucosa sampling procedure using swabs, such as mild bleeding of the nasal mucosa, pharyngeal pain after the sample is taken, sneezing, cough, and gag reflex when taking the pharyngeal mucosa sample. There are no known risks for patients related to the Salivette® Cortisol device, and even accidental ingestion of the device has not led to any adverse reactions being reported, as it is made of inert material and does not contain any active or reactive substances.

[figure not shown]
Sample taking with swab/Salivette® Cortisol

SARS-CoV-2 sampling:

The nasopharyngeal mucosa swab samples and those taken with the Salivette® Cortisol device will be collected in line with the SARS-CoV-2 biological sample collection standards in place at the Research Site.

Sampling

1. Only the health care staff and the individual undergoing the test should be in the room when the test is performed.
2. All of the non-aerosol generating procedures (documentation, interviews, blood sampling) must be performed first. The aerosol generating procedures (collection of oropharyngeal swab samples and saliva samples) must be the final activity performed.
3. It is likely that the collection of oropharyngeal swab samples will cause a cough
4. All samples must be identified with a unique code, using a permanent marker or a label
5. The identities of all samples must be listed separately, without including additional personal data of the patients alongside the samples
6. Collection of oropharyngeal swab samples
 1. Use a tongue depressor to prevent the tongue from interfering with the sample collection
 2. Insert the swab into the mouth
 3. Rub the swab on the tonsillar pillars and the posterior oropharynx, avoiding contact with the tongue, teeth and gums.

4. Place the swab in the sterile viral transport tube and remove the applicator. Ensure that the cap is tightly sealed.

[figure not shown]

5. Transfer the closed tube into a biohazard transportation bag and store the sample in a refrigerator (2-8°C) or freeze the tubes (< 20°C).

7. Saliva (Salivette® Cortisol)

1. Instructions for use

Blue Salivette

...and replace the cap (see Fig. 5).

Sample transportation

The biological samples obtained from the participant will be processed at a central laboratory in Germany, as described in section 2.1.4 TEST METHODS, and transported from Mexico in cold chain to ensure their stability. Sample transportation will be carried out in line with IATA specifications as category B biological samples.

1. Classification: UN3373 Biological Substance, Category B
2. Correct name for shipping: **UN3373 Biological Substance, Category B**
3. Packaging for international transportation: Samples must be packaged, shipped and transported in line with the current edition of the International Air Transport Association (IATA) Dangerous Goods Regulation: packing instruction 6504.
4. Swab sample tubes to be sent between 4 and 8 degrees Celsius or in dry ice, as indicated by the carrier depending on the transportation time. (see section 2.1.6 Storage and transportation conditions – Mexico to Germany).
5. Each shipment must contain a full list of every sample's identity.
6. To ensure the traceability of the shipments, all of these will be organised by the receiving [REDACTED] in [REDACTED] using the World Courier service.

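### The order of throat swab and Salivette is neither varied nor recorded, so any carry-over from the listed swab-first sequence is confounded with the saliva-versus-swab comparison

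*Combined protocol and SAP*

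**What the plan says.** All of the following is in Section 1.4 of the combined protocol and SAP unless stated otherwise.

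- Sampling item 2 puts both collections at the end of the visit: "The aerosol generating procedures (collection of oropharyngeal swab samples and saliva samples) must be the final activity performed". It names the swab before the saliva but does not say which is taken first.
- Item 3 anticipates a reaction to the swab: "It is likely that the collection of oropharyngeal swab samples will cause a cough". The paragraph on procedural risks adds "sneezing, cough, and gag reflex when taking the pharyngeal mucosa sample".
- The swab comes first in the list, "6. Collection of oropharyngeal swab samples", with the instruction "Rub the swab on the tonsillar pillars and the posterior oropharynx, avoiding contact with the tongue, teeth and gums". The saliva sample follows as "7. Saliva (Salivette® Cortisol".
- The Salivette is "placed in the mouth and gently chewed for approximately 60 seconds".
- The only readable safeguard on what enters the mouth before saliva collection is in Section 2.3.1, which excludes food and medicines for 30 minutes beforehand. It does not mention the swab.
- The Introduction gives the use in view: "a method that could be performed at home and during quarantine will prevent the spread".

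The Protocol Summary plans a single sampling per participant, with a direct descriptive comparison of the results. Section 3 gives 20 to 80 participants without a sample size calculation.

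**The concern.** Each participant gives both specimens, and the aim is to show that saliva collected with the Salivette matches the throat swab in reliability. Such a paired comparison is clean only if taking one specimen does not alter the other, or if the order is arranged so that an alteration can be seen.

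Here the procedure listed first rubs the throat and is expected to provoke coughing. A device that absorbs whatever is in the mouth is then chewed. Throat material could reach the saliva specimen because of the comparator procedure. In home use no swab would come first.

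The participants to be counted are SARS-CoV-2 positive, so such carry-over would tend to turn saliva misses into agreement with the swab. That favours the conclusion the programme hopes to reach. With one sampling occasion and no recorded order, the data would offer no way to look for the effect. It would be a systematic error, so enrolling 80 rather than 20 participants would not reduce it.

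**Working it through.** **What the text establishes.** Three things are needed for the concern.

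1. A listed sequence of swab then saliva: present, at items 6 and 7, with the same naming order in item 2.
2. A mechanism: present as a possibility. A cough is expected, a gag reflex is listed, and the saliva device is then chewed for about 60 seconds.
3. No control or record of the order: none in the readable text. The 30-minute rule shows that the protocol regards prior mouth contents as relevant to the saliva result, but it does not cover the swab.

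**Possible size.** The plan has no detection rates, margin or power to reproduce, so every rate here is an assumption.

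- T = 0.90, swab detection in infected participants.
- S = 0.80, saliva detection without a preceding swab.
- c = 0.25 to 0.50, the share of swab-positive/saliva-negative participants whose saliva turns positive through carry-over.
- D = the swab-positive/saliva-negative proportion without carry-over.

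D depends on how the two results are related:

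- Independent: D = (1 − S) × T = 0.20 × 0.90 = 0.18.
- Nested (every saliva positive is also swab positive): D = T − S = 0.90 − 0.80 = 0.10.

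Inflation = c × D. Apparent saliva detection = S + c × D. Apparent deficit = T − (S + c × D), against a true deficit of 10 points.

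| Relation | c | Inflation | Apparent saliva | Apparent deficit | Extra positives, N = 20 / 80 |
|---|---|---|---|---|---|
| Nested | 0.25 | 2.5 points | 82.5% | 7.5 points | 0.5 / 2.0 |
| Nested | 0.50 | 5.0 points | 85.0% | 5.0 points | 1.0 / 4.0 |
| Independent | 0.25 | 4.5 points | 84.5% | 5.5 points | 0.9 / 3.6 |
| Independent | 0.50 | 9.0 points | 89.0% | 1.0 point | 1.8 / 7.2 |

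Over wider assumptions (T 0.90 to 0.95, S 0.70 to 0.85, c 0.10 to 0.50) the inflation runs from 0.5 to 14.3 points.

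**Scale against sampling error.** The exact 95% confidence interval for 80% observed detection is 56% to 94% with 20 participants and 70% to 88% with 80.

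**What alternation could show.** Take 80 participants, 40 per order, and assume that Salivette-first leaves the swab unaffected. With independent results and c = 0.50, the expected swab-positive/saliva-negative pairs are 40 × 0.18 = 7.2 when the Salivette is first and 7.2 × 0.50 = 3.6 when the swab is first. With 20 participants the counts are 10 × 0.18 = 1.8 and 0.9. The contrast can be displayed, but it would seldom be clear statistically.

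**The case against.** **The list is not an instruction about sequence.** Item 2 requires only that the two collections together come last. Items 1 and 3 to 5 are general rules on room occupancy, coughing, labelling and listing, so items 6 and 7 may be instructions per specimen type. This stands: a reader might infer that the protocol mandates swab first, and it does not. But staff may well follow a numbered list, and if they do not, the order varies unrecorded. In neither case can an order effect be examined.

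**The order may be set elsewhere.** Section 1.4 defers to the research site's own collection standards, which are not reproduced, and part of the Salivette instructions and the figures could not be read. This also stands, and limits the point to the readable text.

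**The direction is not established.** The cough remark sits among infection-control rules, and no data on carry-over are given. Prior swabbing could remove material and lower saliva yield. Cough is also a COVID-19 symptom (Section 1.1), so throat material may reach the mouth in home use too. A reader might conclude that saliva detection will be inflated; the documents support only that it could be.

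**The size is easily overstated.** Treating every saliva miss as convertible gives 0.20 × 0.25 = 5 points to 0.20 × 0.50 = 10 points, and the upper end would erase the assumed deficit. That includes participants whose swab was also negative: 0.20 × 0.10 = 2% of participants under independence, 10% under nesting. In them there is little reason to expect detectable throat material to carry over, so the smaller figures in the table are the fair ones.

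**Taking saliva first is not a neutral cure.** Section 1.3 says the device was chosen partly because it stimulates salivation strongly. Chewing it for about 60 seconds could dilute or remove throat material and lower swab yield, again favouring saliva. Avoiding tongue, teeth and gums with the swab does not prevent that. A mandatory saliva-first rule is therefore a trade-off.

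**Conclusion.** The concern holds in a limited form. The protocol lists the cough-provoking comparator before the saliva sample, and its readable text neither varies nor records the order nor sets an interval. If sites follow the list, order and matrix are fully confounded, and the effect cannot be examined afterwards.

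Under the assumed 80% and 90% detection and 25% to 50% conversion of swab-positive/saliva-negative participants, saliva would be inflated by 2.5 to 5.0 points (nested) or 4.5 to 9.0 points (independent). Whether carry-over occurs, in which direction and how often are all assumptions. The documents do not support saying that the order is fixed as swab first, or that the saliva results will be biased upward. The point is a cheap design improvement and does not by itself invalidate the comparison.

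**What to change.** In Sampling items 2, 6 and 7, state that the order of swab and Salivette alternates by participant number (for example, odd numbers swab first and even numbers Salivette first). Record the order used and the collection time of each specimen. In the descriptive analysis, give the paired swab-by-saliva table separately for each order, with the discordant pairs shown. If site standards already set an order, reconcile them with this section.

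The cost is one extra instruction and one time field per specimen, with no additional procedure for the participant. There are two limits:

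- Power to detect an order effect is low with 20 to 80 participants.
- With equal numbers per order and no effect of the Salivette on the swab, pooled results would still carry half the inflation: 1.25 to 2.5 points (nested) or 2.25 to 4.5 points (independent) under the assumptions above. Results by order should therefore accompany the pooled figure. The Salivette-first half is the one closest to saliva-only use.

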2. OBJECTIVES AND GOALS

2.1 MAIN OBJECTIVES AND PRIMARY GOALS

2.1.1 Main objectives

The main objective of the tests is to establish saliva collection with Salivette® Cortisol.

For PCR:

Real-time RT-PCR (██████████)	+/-
Real-time RT-PCR ██████████	+/-

2.1.2 Main diagnosis for admission

Suspected or confirmed cases of SARS-CoV-2 infections (including COVID-19), confirmed with PCR within the past five days.

2.1.3 Inclusion criteria

Only participants who meet the following criteria will be included in the programme:

1. Informed consent form signed and dated before any samples have been taken.
2. Suspected or confirmed SARS-CoV-2 infection by PCR within the past five days.
3. Male and/or female patients aged 18 years and over.

2.1.4 Withdrawal of consent or decision by BI to discontinue the test programme

Participants may withdraw their consent to participate at any time, without having to justify their decision.

2.2 TEST METHODS

The *in vitro* diagnostics have CE marking, are commercially available and are established for diagnostic purposes at the laboratories indicated. They were selected based on their reported sensitivity and specificity criteria, as well as their availability on the market. The laboratory ██████████ was chosen due to being a professional, certified laboratory which is highly experienced in serology methods and with experience in COVID-19 diagnostics since the start of the SARS-CoV-2 pandemic.

2.2.1 Identity of the *in vitro* diagnosis at BI

The test product characteristics are shown below:

Name: **Kylt® for detection/confirmation of SARS-CoV-2**

Method: Real-time RT-PCR

Source: [REDACTED]

Diagnosis site: [REDACTED]

Sample: Swab (throat) and Salivette® Cortisol

Duration: 4-6 hours

Name: **cobas® SARS-CoV-2 (PCR) test**

Method: Automated real-time RT-PCR for cobas® systems

Source: [REDACTED]

Diagnosis site: [REDACTED]

Sample: Swab (throat)

Duration: 3 hours

Name: **TaqPath™ COVID-19 CE-IVD RT-PCR kit**

Method: Multiplex RT-PCR

Source: [REDACTED]

Diagnosis site: [REDACTED]

Sample: Salivette® Cortisol

Duration: 4-6 hours

Real-time PCR detection of SARS-CoV-2

For the qualitative detection of SARS-CoV-2, a single-step RT-PCR method based on specific kits for SARS-CoV-2 or kits which include a primer and a probe (RT-PCR assay).

RT-PCR assays are suitable for implementing a multiplex RT-PCR focus in real time: in the case of a reaction, the RNA target sequences of the gene(s) of interest (e.g., SARS-CoV-2), and an endogenous control (e.g., β-actin) or an IPC (e.g., RNA phage control), are reversely transcribed and amplified in parallel with the corresponding pairs of primers in the polymerase chain reaction. The amplified target gene fragments are detected using probes marked with fluorescence during the real-time PCR reaction. In order to monitor each analysis run, general controls will be provided for performing the run (e.g. positive control and negative control of synthesis).

The specific probes for the gene(s) of interest and the internal control(s) (endogenous or loaded) are each marked with different fluorescent dyes (e.g. FAM and HEX), and their fluorescence emitted is optically measured separately with the real-time PCR thermocycler. Through the individual analyses in one reaction vessel per sample and the positive and negative controls per run, the status of a sample can be evaluated in terms of the gene(s) of interest [Corman et al. 2020].

